| CSR | Clinical Study Report |
| CTU | Clinical Trial Unit |
| CV% | Coefficient of Variation |
| DCC | Data Coordinating Center |
| DMID | Division of Microbiology and Infectious Diseases |
| DNA | Deoxyribonucleic acid |
| eCRF | Electronic Case Report Form |
| EC | Ethics Committee |
| ECG | Electrocardiogram |
| EDC | Electronic Data Capture |
| ET | Early Termination |

| | |
|---------------------|--|
| FDA | Food and Drug Administration |
| FSH | Follicle-stimulating hormone |
| FWA | Federalwide Assurance |
| g | Gram(s) |
| GCP | Good Clinical Practice |
| g/dL | Gram(s) per Deciliter |
| h | Hour(s) |
| HBsAg | Hepatitis B Surface Antigen |
| HCG (β -HCG) | Human Chorionic Gonadotropic Hormone |
| Hct | Hematocrit |
| Hgb | Hemoglobin |
| HCV | Hepatitis C Virus |
| HEENT | Head, Eyes, Ears, Nose, and Throat |
| HIV | Human Immunodeficiency Virus |
| HPLC-MS/MS | High-Performance Liquid Chromatography with Tandem Mass Spectrometry |
| HR | Heart Rate |
| IB | Investigator's Brochure |
| IC ₅₀ | 50% Inhibitory Concentration |
| ICF | Informed Consent Form |
| ICH | International Conference on Harmonization |
| ICMJE | International Committee of Medical Journal Editors |
| IM | Intramuscular |
| IND | Investigational New Drug |
| IRB | Institutional Review Board |
| ISM | Independent Safety Monitor |
| IV | Intravenous |
| kg | Kilogram |
| LLN | Lower Limit of Normal |
| MDMA | 3,4-methylenedioxy-methamphetamine |
| MedDRA [®] | Medical Dictionary for Regulatory Activities |

| | |
|--------|---|
| MH | Medical History |
| µg | Microgram(s) |
| µM | Micromolar |
| µmol | Micromole(s) |
| mg | Milligram(s) |
| mg/dl | Milligram(s) per Deciliter |
| MIC | Minimum Inhibitory Concentration |
| mL | Milliliter(s) |
| mm | Millimeter(s) |
| MM | Medical monitor |
| MMA | Mouse Micronucleus Aberration Assay |
| mmHg | Millimeters of Mercury |
| min | Minute(s) |
| MOP | Manual of Procedures |
| msec | Milliseconds(s) |
| NIAID | National Institute of Allergy and Infectious Diseases |
| NIH | National Institutes of Health |
| NOAEL | No observable adverse effect level |
| NSAIDs | Nonsteroidal Anti-Inflammatory Drugs |
| OCRR | Office of Clinical Research Resources |
| PD | Pharmacodynamic(s) |
| PE | Physical Examination |
| PI | Principal Investigator |
| PK | Pharmacokinetics |
| PO | Oral |
| POC | Point of Contact |
| PVG | Pharmacovigilance Group |
| QTc | Corrected QT Interval |
| RBC | Red Blood Cell |
| RP | Research Pharmacist |
| SAE | Serious Adverse Event |

| | |
|------------------|--------------------------------------|
| SAP | Statistical Analysis Plan |
| sec | Second(s) |
| SMC | Safety Monitoring Committee |
| T _{max} | Time to Maximum Plasma Concentration |
| TCA | Tricyclic antidepressants |
| UA | Urinalysis |
| VS | Vital Signs |
| ULN | Upper Limit of Normal |
| WBC | White Blood Cell Count |
| WHO | World Health Organization |

PROTOCOL SUMMARY

- Title:** A Phase 1 Clinical Trial to Evaluate the Plasma Pharmacokinetics (PK), Safety, and Tolerability of a Single Oral Dose of Zoliflodacin in Healthy Male and Female Subjects
- Phase:** 1
- Population:** Eight healthy male and female subjects aged 18 to 45 years inclusive
- Number of Sites:** One (IQVIA Phase One Services, LLC, Overland Park, KS)
- Study Duration:** Approximately 4 weeks
- Subject Participation Duration:** Up to 10 days (from dosing to final visit)
- Description of Agents:** The study drug, zoliflodacin (also known as AZD0914 and ETX0914), is a spiroprymidinetrione antibacterial agent. Its chemical name is (2R,4S,4aS)-11-fluoro-2,4-dimethyl-8-[(4S)-4-methyl-2-oxo-1,3-oxazolidin-3-yl]-1,2,4,4a-tetrahydro-2'H,6H-spiro[1,4-oxazino[4,3-a][1,2]oxazolo[4,5-g]quinoline-5,5'-pyrimidine]-2',4',6'(1'H,3'H)-trione. It is formulated as a powder in sachets containing 2 grams (g) of the active agent and inactive excipients.
- Objectives:**
- Primary:**
- To evaluate the plasma PK of zoliflodacin after administration of a single 4-g oral dose under fasting conditions
- Secondary:**
- To evaluate the safety and tolerability of a single 4-g oral dose of zoliflodacin
- Outcome Measures:**
- Primary:** C_{max} , T_{max} , $AUC_{(0-last)}$, and other PK parameters for zoliflodacin determined using plasma concentrations of zoliflodacin in blood samples collected on Day 1 [baseline (30 min before dosing) and 0.5 h, 1 h, 2 h, 3 h, 4 h, 6 h, 8 h, and 12 h after dosing], Day 2 [24 h and 36 h after dosing], Day 3 [48 h after dosing], and Day 4 [72 h after dosing],

or early termination (ET), and measured using a validated HPLC-MS/MS method

Secondary:

- The occurrence of treatment-emergent serious adverse events (SAEs) from administration of zoliflodacin on Day 1 to Final Visit (Day 8 ± 2), or ET
- The occurrence of unsolicited treatment-emergent adverse events (AEs) from administration of zoliflodacin on Day 1 to Final Visit (Day 8 ± 2), or ET
- The changes from baseline (up to 60 min before dosing) in vital signs (VS) following administration of zoliflodacin, as measured on Day 1 [1 h, 2 h, and 4 h after dosing], Days 2, 3, and 4 [24 h, 48 h, and 72 h, respectively, after dosing], and Final Visit (Day 8 ± 2), or ET
- The changes from baseline (Day -1) in clinical laboratory values following administration of zoliflodacin, as measured on Day 4, or ET
- The changes from baseline (up to 60 min before dosing) in electrocardiogram (ECG) parameters following administration of zoliflodacin, as measured on Day 1 [1 h, 2 h, and 4 h after dosing] and Day 4 [72 h after dosing], or ET

Description of Study Design:

The trial is an open-label, non-randomized evaluation of the PK and safety profiles of a single 4-g oral dose of zoliflodacin in eight healthy male or female subjects. Each subject will receive zoliflodacin reconstituted in [REDACTED] after at least an 8-h fast, which will continue for at least 4 h after dosing. Consumption of water is permitted during the fasting period. All subjects will be dosed in the morning of Day 1 in a staggered fashion with a minimum of several minutes apart.

Subjects who consent to participate will be enrolled in the trial if they meet all of the inclusion and none of the exclusion eligibility criteria. Laboratory assessments at Screening Visit will include testing for serology [human immunodeficiency virus (HIV), hepatitis B surface antigen (HBsAg), and hepatitis C virus (HCV)], drugs of abuse, and alcohol. Serum pregnancy testing will be done in all females and serum FSH levels will be measured only in post-menopausal females. Safety assessments at scheduled visits will include medical history (MH), vital signs (VS), physical examination (PE), 12-lead ECG, and clinical laboratory values including complete blood count (CBC) with differential, comprehensive metabolic (chemistry) panel, and urinalysis (UA) for blood, glucose, and protein. Treatment-emergent AEs and SAEs will be assessed from the time of dosing to the end of the trial. Plasma

for PK analysis will be collected at scheduled time points before and after dosing on Day 1 and through Day 4, or ET.

Estimated Time to Complete Enrollment: Up to 10 days (from dosing to last visit)

Halting Criteria Decision Process: If criteria for halting the trial (as listed in [Section 9.5.1](#)) are met during dosing on Day 1 prior to all subjects being dosed, an *ad hoc* Safety Monitoring Committee (SMC) meeting will be held to review all available safety data and to make recommendations about the dosing of all further subjects in the trial. A scheduled SMC meeting will be held after all subjects complete the trial to review all safety data, and advise on using the 4-g dose in a subsequent thorough QTc study.

2 BACKGROUND INFORMATION AND SCIENTIFIC RATIONALE

2.1 Background Information

2.1.1 Overview of the Disease: Gonorrhea and its Treatment

Neisseria gonorrhoeae, currently the second most common bacterial sexually transmitted infection worldwide (after *Chlamydia trachomatis*), is a serious public health problem.^{1,2} In 2008, the World Health Organization (WHO) estimated 106 million cases of gonorrhea among adults worldwide.³ In 2012, the Centers for Disease Control and Prevention (CDC) reported 311,404 cases of gonorrhea in the US; however, due to incomplete reporting, up to 820,000 cases may occur annually.⁴ *N. gonorrhoeae* has developed resistance to all antimicrobial treatments for gonorrhea. The CDC recently released its report “Antibiotic Resistance Threats in the US, 2013,” which ranks drug-resistant *N. gonorrhoeae* as an “Urgent Threat,” defined as “an immediate public health threat that requires urgent and aggressive action.”⁵ This level of resistance has demanded alternative oral treatments, which until recently have been readily available.⁶ Examples of drug classes that are widely used to treat gonorrhea, but are no longer recommended as monotherapy due to resistance, include sulfanilamides, penicillin, tetracyclines, and fluoroquinolones.^{1,2} Most recently, *N. gonorrhoeae* resistance to macrolides (including azithromycin), cefixime, and ceftriaxone, and consequent clinical failures, have been reported. Since two extended-spectrum cephalosporins, ceftriaxone and cefixime, have recently been the only first-line options for treating gonorrhea, resistance and treatment failures with these drugs are particularly concerning. It is only a matter of time before gonococci with full resistance to extended-spectrum cephalosporins emerge and spread globally.⁷ The threat of widespread ceftriaxone resistance and untreatable *N. gonorrhoeae* infection is real.^{5,6} The clinical development of zoliflodacin (also known as AZD0914 and ETX0914) addresses the need for new antibiotics that can be used alone or with other agents to treat uncomplicated gonorrhea caused by emergent *N. gonorrhoeae* strains that are resistant to existing antibiotics.^{8,9}

2.1.2 Zoliflodacin Development

Zoliflodacin is a spiropyrimidinetrione antibacterial drug, which inhibits bacterial DNA synthesis by a novel mechanism. Zoliflodacin demonstrates *in vitro* activity against *N. gonorrhoeae* strains that are susceptible or resistant to current available therapies and *in vivo* efficacy, including in patients with uncomplicated gonorrhea.^{8,9,10,11}

This section provides a summary of zoliflodacin. Nonclinical and clinical data are provided in more detail in the Investigator’s Brochure (IB).

Chemistry

The chemical name for zoliflodacin is (2R,4S,4aS)-11-fluoro-2,4-dimethyl-8-[(4S)-4-methyl-2-oxo-1,3-oxazolidin-3-yl]-1,2,4,4a-tetrahydro-2'H,6H-spiro[1,4-oxazino[4,3-a][1,2]oxazolo[4,5-g]quinoline-5,5'-pyrimidine]-2',4',6'(1'H,3'H)-trione.

Mechanism of Action

Zoliflodacin inhibits bacterial Type II topoisomerases, specifically bacterial gyrases. The activity and mode of inhibition of bacterial gyrase by zoliflodacin has been assessed in several *in vitro* assays. Zoliflodacin stabilizes the [REDACTED], but in addition prevents its [REDACTED]. [REDACTED] is further supported [REDACTED]. [REDACTED] *N. gonorrhoeae* resistance to [REDACTED].⁸

Microbiological Activity

In vitro: Zoliflodacin has demonstrated activity *in vitro* against *N. gonorrhoeae*, including strains that are resistant to penicillin, ciprofloxacin, tetracycline, azithromycin, ceftriaxone, and cefixime. Minimum inhibitory concentration (MIC)₉₀ values ranged from 0.125 to 0.25 µg/mL. Zoliflodacin has also shown bactericidal activity at an MIC₉₀ of 0.25 µg/mL against *C. trachomatis*, which often co-infects patients with gonorrhea.^{8,9,10}

In vivo: Mouse model of Staphylococcus aureus infection: An animal model for *N. gonorrhoeae* has not been established due to spontaneous bacterial eradication. To estimate a human efficacious exposure of zoliflodacin for *N. gonorrhoeae*, a surrogate pathogen approach, which utilizes pharmacokinetics/pharmacodynamics (PK/PD) determinations from a *S. aureus* neutropenic mouse thigh model that correlates with human clinical efficacy, was used. In this model, zoliflodacin was efficacious *in vivo* against clinical *S. aureus* isolates. The MIC values of zoliflodacin against *S. aureus* and *N. gonorrhoeae* and the clinical doses suggest that efficacy can be translated across pathogens based on AUC/MIC targets. From this analysis, the efficacious human exposure for zoliflodacin was estimated utilizing a PK/PD target that covers a mean fAUC/MIC of 66 (range 43–98) for *S. aureus* in the mouse thigh model. This target, combined with the MIC₉₀ of zoliflodacin for *N. gonorrhoeae* and the human unbound fraction (f_u) of 17%, translated to a predicted efficacious mean AUC in humans of 49 µg*h/mL.^{8,9}

In vivo: Human Phase 2 trial: Zoliflodacin was recently investigated in a multi-center, randomized, Phase 2 trial to assess the safety and efficacy of zoliflodacin administered orally to adults to treat uncomplicated urogenital gonorrhea compared to treatment with ceftriaxone administered intramuscularly. Subjects were randomly assigned to receive a single oral dose of 2 g of zoliflodacin, 3 g of zoliflodacin, or a single intramuscular (IM) dose of 500 mg of

ceftriaxone. In the per-protocol population, microbiological cure was observed [REDACTED] [REDACTED].⁸

Human Pharmacokinetics

A single-center, multi-part, Phase 1 trial with an oral suspension of zoliflodacin versus placebo was conducted in healthy men and women. In part A, 48 subjects received single ascending doses of zoliflodacin ranging from 200 mg to 4 g, or placebo (6:2, zoliflodacin:placebo). In Part B, zoliflodacin was administered in doses of 1.5 g (N=8) and 3 g (N=10) to evaluate the effect of food on the PK of zoliflodacin. Zoliflodacin was absorbed relatively quickly under fasting conditions, with a median T_{max} ranging from [REDACTED]. Following C_{max} , plasma drug concentrations [REDACTED]. The terminal elimination phase started at approximately [REDACTED], zoliflodacin concentrations declined with a half-life ranging from [REDACTED]. Exposures [REDACTED], suggesting a [REDACTED]. When [REDACTED] of zoliflodacin was administered, a [REDACTED] was seen if the drug was [REDACTED]. The C_{max} [REDACTED] consistent with [REDACTED].⁸

In a Phase 2 trial of patients with gonorrhea, [REDACTED]. The AUC and C_{max} values for zoliflodacin at the various doses also point to a margin of safety, as seen by multiples to rat and dog NOAEL (no observable adverse effect level) values.⁸

Potential for Drug-Drug Interactions

Zoliflodacin is a [REDACTED] in preclinical studies. *In vitro* and *in vivo* metabolism across species indicate that the compound is [REDACTED]. As a single dose therapy with no evidence of [REDACTED], the compound is not expected to show lasting effects. The potential for drug-drug interactions has been evaluated using a physiologically-based PK model developed with the [REDACTED].⁸ In summary:

1. Zoliflodacin as a victim: Single doses of zoliflodacin ranging from [REDACTED] [REDACTED] [REDACTED] [REDACTED] [REDACTED] [REDACTED] [REDACTED] [REDACTED]. The primary

PK driver for efficacy of zoliflodacin is [REDACTED].

2. Zoliflodacin as a perpetrator: Zoliflodacin is predicted to [REDACTED]. The extent of the interaction is not predicted to differ between the zoliflodacin [REDACTED]. This [REDACTED] administration of zoliflodacin.

Safety

In vitro studies: There was no [REDACTED]. There was no inhibition of [REDACTED].

Some fluoroquinolones induce QT prolongation leading to arrhythmias and torsades de pointes, which have been correlated with binding to the hERG K⁺ channel. In contrast, zoliflodacin showed [REDACTED].

Animal pharmacology and toxicology studies: Zoliflodacin was well tolerated – as a [REDACTED]. There was [REDACTED]. At this highest dose tested, [REDACTED].

[REDACTED] These effects were [REDACTED]. There were [REDACTED].

[REDACTED]
[REDACTED].⁸

Effects of zoliflodacin on female fertility and embryofetal development have been assessed [REDACTED]
[REDACTED] Effects on [REDACTED]
Following administration of zoliflodacin at doses of [REDACTED]

[REDACTED]
[REDACTED]

[REDACTED]. At all dose levels, there were [REDACTED]
[REDACTED]

[REDACTED]
[REDACTED]
[REDACTED]
[REDACTED]
[REDACTED]

The effects of zoliflodacin on male fertility have been assessed [REDACTED]
[REDACTED] Administration at [REDACTED]

[REDACTED]
[REDACTED]
[REDACTED]
[REDACTED].

Human trials: Three trials have evaluated the safety of zoliflodacin in humans.⁸

In healthy subjects in the Phase 1 trials, [REDACTED]
[REDACTED]
[REDACTED]
[REDACTED].^{8,12}

In patients in the Phase 2 trial, zoliflodacin was generally safe and well tolerated. AEs reported were generally mild, were non-serious, and none led to trial discontinuation. The AE and laboratory safety profiles of zoliflodacin were generally similar to those of ceftriaxone. The AE profile of zoliflodacin 2 g was generally similar to that of zoliflodacin 3 g; headache was more common in the zoliflodacin 3-g group (9%) compared to the zoliflodacin 2-g group (0%). Dysgeusia was not reported in the Phase 2 trial. Vomiting was reported by one patient receiving zoliflodacin 3 g.^{8,13}

There were no AEs reported at a frequency of $\geq 5\%$ when the AE profiles of the zoliflodacin 2-g and zoliflodacin 3-g groups were combined. The most common AEs reported with zoliflodacin ($\geq 3\%$ based on the zoliflodacin 2-g and zoliflodacin 3g groups combined and excluding infection-related AEs) were diarrhea, headache, and nausea.^{8,13}

2.2 Rationale

2.2.1 Rationale for Use of Zoliflodacin

A single PO dose of zoliflodacin has been shown to be effective against uncomplicated gonorrhea caused by *N. gonorrhoeae* strains susceptible or resistant to currently available therapies. These findings supported the ongoing clinical development of zoliflodacin as a potential new therapeutic option for uncomplicated gonorrhea. The recently completed Phase 2 clinical trial suggests that zoliflodacin doses in the range of 2 g to 3 g are therapeutic. The present clinical trial will further characterize the PK characteristics and safety profile of a high 4-g dose of zoliflodacin and evaluate whether it can be used in a planned thorough QTc study.

2.2.2 Rationale for Dose Selection

Regulatory guidance ICH/FDA E14 has emphasized the need to obtain robust data on the effect of new chemical entities on ECG parameters, focusing on cardiac repolarization as measured by the QTc.¹⁴ To obtain these data, the potential of a single therapeutic dose and a single suprathreshold dose of the study drug to prolong cardiac repolarization is measured. The 4-g dose of a previous formulation of zoliflodacin was found to be safe and well tolerated in a Phase 1 trial. The current trial will further characterize the PK and safety profiles of the 4-g dose of a new zoliflodacin formulation. This dose could result in drug exposures that are multiples of the proposed 2-g therapeutic dose and meet the requirements for a suprathreshold dose according to the ICH/FDA E14 Guidance for thorough QTc studies.¹⁴

2.3 Identified and Potential Risks and Benefits

2.3.1 Identified Risks

Single zoliflodacin doses ranging from 200 mg to 4 g were generally safe and well tolerated in the Phase 1 and Phase 2 clinical trials conducted to date in healthy subjects and patients with uncomplicated gonorrhea.^{8,12,13} The most common AEs reported with zoliflodacin in the Phase 1 trials were dysgeusia and headache, and in the Phase 2 trial ($\geq 3\%$ based on the zoliflodacin 2-g and zoliflodacin 3-g groups combined and excluding infection-related AEs) were diarrhea, headache, and nausea. These events will continue to be monitored and evaluated.

2.3.2 Potential Risks

The potential risks to subjects participating in the trial are those related to PO dosing of zoliflodacin, and associated study procedures (venipuncture, IV catheter insertion, ECG patch application, and blood sampling).

Zoliflodacin-Associated Risks

As for any drug, exposure to zoliflodacin could result in an allergic or hypersensitivity reaction that could be mild or life-threatening. Should a reaction occur, medically-appropriate diagnostic and therapeutic measures will be taken immediately by trained site clinicians and staff.

In a Phase 1 trial, analysis of [REDACTED]
[REDACTED]
[REDACTED].

Monitoring of [REDACTED] will continue in the trial.

In a Phase 1 and Phase 2 trial, no trends [REDACTED]
[REDACTED].

Standard clinical monitoring of [REDACTED]
[REDACTED]
[REDACTED]

[REDACTED] The incidence of these findings typically [REDACTED]

[REDACTED]
[REDACTED]
[REDACTED]
[REDACTED]

[REDACTED] in the first-in-human trial. [REDACTED]

[REDACTED]. These findings are not considered to preclude administration of zoliflodacin to healthy male subjects with appropriate informed consent.

Effects of chronic dosing of zoliflodacin on [REDACTED]
[REDACTED]. With respect to [REDACTED]

[REDACTED]
[REDACTED]
[REDACTED]
[REDACTED]
[REDACTED]
[REDACTED]

[REDACTED]. The effects of zoliflodacin [REDACTED]
[REDACTED]

[REDACTED] Based on these preclinical data and the gonorrheal clinical indication, in current and future clinical trials:

- Female subjects will be pregnancy tested prior to administration of zoliflodacin and at the end of the trial and will be required to use specified birth control methods for 30 days following final study visit.

- Male subjects will be required to use specified birth control methods for 90 days following final study visit and will be advised not to donate sperm during this period.

Venipuncture and IV Catheter Placement Risks

Venipuncture: Venipuncture causes transient discomfort and may cause fainting. Bruising at the site of venipuncture may occur, but can be prevented or lessened by applying pressure for several min. Infection at the site is possible but highly unlikely as aseptic technique will be used.

IV catheter placement: An indwelling catheter may be placed in an arm vein (preferably antecubital) for frequent blood drawing for PK measurements. The catheter may cause phlebitis with signs of redness and warmth at or near the IV insertion site, and thrombophlebitis with a hard area palpable near the IV insertion site. These risks are minimal as the IV catheters, when used, are only used briefly after dosing. Careful inspection of the catheter site, including visualization of blood return, and withdrawal of the catheter if needed will minimize this risk. There is a risk of infection; however, this is a small risk as aseptic technique will be used.

Additional Risks

ECG: Possible side effects from ECG patches include a rash or minor irritation of the skin.

Blood draws: The amount of blood drawn is about 18 mL during the Screening Visit and Day -1 period, 74 mL during the inpatient period (Days 1-4), and 92 mL during the entire trial ([Appendix D](#)). Additionally, small amounts of blood loss may occur if an IV catheter is used or additional blood samples are collected (for repeat laboratory testing, evaluation of AE, etc.). Overall, the amount of blood that may be drawn during the trial is within the amount that considered safe to be drawn during short or extended periods, respectively, and not excessive for the safety and PK assessment requirements of Phase 1 trials. However, there is a small risk that some subjects may develop mild symptoms of hypovolemia or anemia during the trial. These are reversible with specific treatment (fluid replacement, good nutrition, vitamins, or iron supplementation).

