7.3 Enrollment/Baseline

7.3.1 Admission Visit (Day -1, Unit Check-in)

Subjects meeting all of the inclusion and none of the exclusion criteria at Screening Visit will check into the CTU on Day -1 and the following procedures will be performed:

- Review inclusion/exclusion criteria to ensure the subject remains eligible for enrollment
- Update MH
- Update Prior Medications
- Perform abbreviated PE (An abbreviated complete PE will be performed if the Screening PE was completed >7 days from dosing)
- Obtain VS
- Obtain weight
- Obtain blood and urine samples for clinical laboratory tests (if screening samples were collected >7days from dosing)
- For all women, a serum β -HCG pregnancy test will be done, and negative results confirmed before dosing
- Obtain urine sample for toxicology
- Perform breathalyzer test for alcohol use
- Obtain 12-lead ECG with 10-sec rhythm strip

Subjects who meet the eligibility criteria on Day -1 will be admitted to the CTU on the same day. The subject will fast at least 8 h before dosing, but will have access to water during that period.

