7.5 Final Study Visit (Day 8 \pm 2)

- Update MH
- Obtain VS
- Perform complete PE
- Obtain weight
- Collect blood for serum β -HCG pregnancy test in all females
- Perform AE and SAE assessments
- Update ConMeds
- Counsel male and female subjects on the avoidance of pregnancy
- Counsel female subjects to use appropriate contraception for 30 days after the final visit.
- Counsel male subjects to use appropriate contraception and refrain from sperm donation for 90 days after the final visit.

- Discharge from trial after review of clinical laboratory tests, ECG, and other assessments by PI or authorized clinician

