8.2 Laboratory Evaluations

Venipuncture schedule and blood volumes are shown in [Appendix A](#) and [Appendix D](#). The blood volume for hematology and chemistry tests will be approximately 9 mL per sample ([Appendix D](#)).

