8.2.1.3 Pregnancy Testing

In all women, a serum β -HCG level will be measured at Screening Visit and on Day -1; results must be negative for entry into the trial. Serum pregnancy test will also be performed at Final Visit, or ET.

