APPENDIX D: BLOOD VOLUME WITHDRAWN DURING THE TRIAL

Laboratory Samples and Estimated Total Blood Volume (mL)

| Study visit | SCREENING | CHECK- IN | INPATIENT PERIOD | | | | FINAL | Total volume | Early term visit |
|--|-----------|--------------|------------------|----|----|-----|--------|--------------|------------------|
| Study Day | -21 to -2 | -1 | 1 | 2 | 3 | 4 | 8 (±2) | | |
| HEMATOLOGY ¹ | 4 | 4 | | | | 4 | | 12 | 4 |
| CHEMISTRY and serum β-HCG, FSH, HIV, HBsAg, HCV ¹ | 5 | 5 | | | | 5 | | 15 | 5 |
| PK ² | | | 54 | 12 | 6 | 6 | | 78 | 6 |
| Total volume/visit | 9 | 9 | 54 | 12 | 6 | 15 | 0 | - | 15 |
| Cumulative total volume | 9 | 18 | 72 | 84 | 90 | 105 | 105 | 105 | |

¹ Clinical blood tests are drawn at Screening Visit, on Day-1, and on Day 4, or ET.

² PK serum samples are drawn on Day 1: 30 min before dosing and at 0.5, 1, 2, 3, 4, 6, 8, 12, 24, 36, 48 and 72 h after dosing, or ET.

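### Does the 13 mL disagreement between Protocol Section 2.3.2 and Appendix D over blood drawn call for a change to the plan?

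*Protocol*

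**What the plan says.** Protocol Section 2.3.2, in the item on blood draws, says "The amount of blood drawn is about 18 mL during the Screening Visit and Day -1 period", then "74 mL during the inpatient period (Days 1-4), and 92 mL during the entire trial", and refers to Appendix D. It goes on to allow for further blood loss from catheter use, repeat testing or evaluation of adverse events. Only then does it say that the amount that may be drawn is within what is considered safe, and it gives no numeric limit.

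Appendix D gives the volumes by visit. Its running total reads "Cumulative total volume | 9 | 18 | 72 | 84 | 90 | 105 | 105 | 105". Its first footnote states "Clinical blood tests are drawn at Screening Visit, on Day-1, and on Day 4, or ET". Section 8.2 adds: "The blood volume for hematology and chemistry tests will be approximately 9 mL per sample".

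For the Final Visit, where Appendix D shows 0 mL, Section 7.5 lists "Collect blood for serum β -HCG pregnancy test in all females". Section 8.2.1.3 agrees: "Serum pregnancy test will also be performed at Final Visit, or ET". The Appendix A schedule also marks a serum pregnancy test at that visit.

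**The concern.** A risk statement that cites a table should match it, and this one does not. The word *about* in Section 2.3.2 cannot cover a 13 mL gap, because the gap is exactly 1 mL for each of the 13 PK samples. That pattern suggests the sample volume was revised in one place and not in the other. The missing Final Visit entry also makes the appendix incomplete for women, although its chemistry row is labelled as including serum β-HCG.

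What could be at stake is the accuracy of the burden described for healthy volunteers, who have no benefit from taking part (Section 2.3.3), and the basis for calling the volume safe. If the lower figure had been compared with a limit, or if a volume fed a rule or an analysis, the mismatch would matter.

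**Working it through.** **Inputs**

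- Section 2.3.2: 18 mL before Day 1, 74 mL on Days 1-4, 92 mL in total.
- Appendix D, hematology: 4 mL at Screening, Day -1 and Day 4.
- Appendix D, chemistry with β-HCG and serology: 5 mL at the same three visits.
- Appendix D, PK: 54, 12, 6 and 6 mL on Days 1 to 4.
- Section 8.2: about 9 mL per hematology and chemistry draw.
- Section 8.2.2.1: 9 PK samples on Day 1, 2 on Day 2, 1 on Day 3 and 1 on Day 4, so 9 + 2 + 1 + 1 = 13.

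**Step 1: the text on its own terms.** 18 + 74 = 92 mL. Section 2.3.2 is internally consistent.

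**Step 2: Appendix D on its own terms.**

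- By row: 12 + 15 + 78 = 105 mL.
- By visit: 9 + 9 + 54 + 12 + 6 + 15 + 0 = 105 mL.
- Running total: 9, 18, 72, 84, 90, 105, 105, as printed.
- Days 1-4: 54 + 12 + 6 + 15 = 87 mL.

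The appendix is also internally consistent, so this is not a broken table.

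**Step 3: the two compared.**

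| Period | Section 2.3.2 | Appendix D | Difference |
|---|---|---|---|
| Screening and Day -1 | 18 mL | 18 mL | 0 |
| Days 1-4 | 74 mL | 87 mL | 13 mL (13/87 = 14.9%) |
| Whole trial | 92 mL | 105 mL | 13 mL (13/105 = 12.4%) |

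**Step 4: where the gap lies.** Take off the Day 4 laboratory draw of 9 mL, on which Section 8.2 and Appendix D agree. The text leaves 74 - 9 = 65 mL for PK and the appendix leaves 87 - 9 = 78 mL. Over 13 samples, 65/13 = 5 mL and 78/13 = 6 mL. The 6 mL follows from Appendix D. The 5 mL is an inference, and no section states it.

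**Step 5: could the skipped Day -1 draw explain it?** Section 7.3.1 omits the Day -1 laboratory samples when the screening samples were taken within 7 days of dosing. That gives 105 - 9 = 96 mL, not 92, and leaves Days 1-4 at 87. It does not explain the gap.

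**Step 6: the Final Visit draw.** It applies to women only and its volume is not stated. If it is assumed to be at most the 5 mL of the combined chemistry and β-HCG row, the scheduled total for women on the Appendix D basis is above 105 mL and at most 105 + 5 = 110 mL.

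**Step 7: does anything use these totals?**

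- Section 2.3.2 compares them with no stated number.
- The halting criteria in Section 9.5.1 concern deaths, adverse events and patterns of events, not blood volume.
- PK sampling (Protocol Section 8.2.2.1; PK SAP Section 2.3) is defined by times, and these agree.
- The PK parameters (Protocol Section 11.4.4; PK SAP Section 3.4) are computed from concentrations, actual times and dose. The volume drawn is not an input.
- The sample size statement (Section 11.2) does not refer to blood volume.

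**The case for a change.** The strongest case for acting is that healthy volunteers without prospect of benefit should have their burden described correctly. The paragraph that calls the volume acceptable gives figures that its own source contradicts, and it acknowledges a small risk of mild hypovolemia or anemia. A reader cannot tell whether 92 or 105 mL was assessed, and for women neither figure includes the Final Visit test. Correcting it would need only a text edit.

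The factual part stands in full: the figures disagree, rounding does not excuse it, and the Final Visit entry is missing.

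The inference to a consequence does not stand. The safety sentence refers to whatever may be drawn during the trial, after allowing for extra samples, and is not derived from 92 mL set against a threshold. The higher figure is printed in the appendix that the text cites. The totals are scheduled volumes, not fixed amounts: they fall if the Day -1 laboratory samples are skipped, and rise with repeat tests (Section 8.2.1.1) or unscheduled visits (Section 7.7). What participants were told cannot be judged, because consent pages are not part of the material under review.

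**Conclusion.** This is a clerical inconsistency, and no change to the plan follows. Section 2.3.2 is 13 mL below Appendix D for Days 1-4 (74 against 87 mL) and for the whole trial (92 against 105 mL). Appendix D also omits one pregnancy-test draw in women, of unstated volume. No endpoint, analysis, sampling time, limit or stopping decision depends on any of these figures, and nothing in the documents shows that the higher total is unsafe.

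The 13 mL gap and the Appendix D totals follow directly from printed numbers. Placing the gap in the PK samples rests on the 9 mL laboratory draw applying in both places. Reading it as 5 mL against 6 mL per sample rests on back-calculation. The ceiling of 110 mL for women rests on an assumed Final Visit draw of no more than 5 mL.
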